### **5.3 Description of the Survey Methods**

We will use a multi-center, cross-sectional patient survey design to systematically collect and compare PROs in patients in the GCC or AS groups. All participants will be asked to complete a one-time, REDCap online survey or a mailed paper survey, depending on patient preference, and a telephone-administered version will be available if necessary.

### **5.4 Data Collection**

PRO data to be collected is described in detail above (Section 5.2). Additional data will be abstracted from the medical record beyond what is needed to determine eligibility, including prior history of breast surgery (lumpectomy, mastectomy, reduction/augmentation, implants, or other surgery, axillary surgery) and known high risk predisposition (e.g., BRCA 1 or 2 positive, prior history of radiation to the chest).

### **5.5 Description of the study process**

#### **5.5.1 Survey Administration**

We will recruit approximately 900 women with DCIS matched 3:1 to women with ADH or LCIS/ALH (proxies for AS group) or DCIS choosing AS identified at 6 geographically and demographically distinct study sites: DUMC, DFCI, MDACC, MGH, NWH, and DFCI @ SSH. Any patients who have selected AS for DCIS will specifically be identified and contacted for inclusion in the study. Enrolled patients will be asked to complete a one-time survey. The recruitment and survey phases will take place over an 18-month period once enrollment begins. We anticipate data cleaning and analysis will last 6 months.

The study coordinator at each site or the lead for an affiliate site will verify the mailing address and/or email address for each eligible patient, then local study staff will send an invitation letter and response form (Appendix A). The invitation letter and response form will include information about the study, study coordinator contact information, and will ask participants to send the local site their email address in order to receive the link to the study materials including an online elements of consent information page and online survey (Appendix B), or their address to receive the consent and survey (Appendix B) via mail. The contact information of all women who agree to participate in the study will be sent from the local study team to the DFCI study team to contact potential participants to initiate the consenting and survey process (Appendix B). In DFCI's initial application, it was requested and approved, to have a waiver of documentation of consent for people who complete the survey online or on the phone.

### **Web-based**

The REDCap survey can be accessed from any computer that has internet; the place of completion will be at the discretion of the participant. Prior to the survey questions in REDCap, participants will read and respond to the screening questions (Appendix E) to determine eligibility before moving to a next page which contains the elements of informed consent (Appendix C). If a participant is ineligible to participate in the study, she will not be able to move on to the informed consent information page. If the participant is eligible, she will proceed to the informed consent information page and then to the survey itself (Appendix B).

### **Print survey**

As an alternative to the on-line survey, patients will be provided the option to complete a survey by mail, or by phone. If completing by mail method, the patient will be mailed two copies of the paper consent, and asked to sign one of the copies and return with the completed survey. The paper version of the survey (Appendix B) will be sent with the screening questions (Appendix E) as a cover page along with the two copies of the paper informed consent form. If the participant answers the screening questions (Appendix E) and is ineligible, she will be instructed to stop and return Appendix E in the enclosed pre-paid, pre-stamped envelope. If the participant is eligible, she will be asked to sign one copy of the consent and return it along with the completed screening questions (Appendix E) as well as the completed survey (Appendix B), which will be attached to one-another for the paper version.

### **Phone survey**

If completing by phone, the study team will first verbally introduce the study, then will administer the screening questions (Appendix E). If the participant is ineligible, study staff will not continue onto the survey. If the participant is eligible, the study coordinator will administer and document verbal consent (Appendix D) and subsequently administer the patient survey (Appendix B).

The online survey will be programmed in REDCap with appropriate skip patterns, and the paper version

will have clear instructions in order to reduce missing data. The paper copy of the survey is submitted as Appendix B. There will be 10 different versions of TTO questions in paper and in REDCap. Participants will be assigned to different versions of TTO (Treatment Trade Off) by the DFCI study team on a rolling basis (e.g. first participant will receive the first version, second participant will receive the second version, and so on). TTO survey is submitted as Appendix G. Patient advocates have piloted both the online and written form of the survey. If the survey needs to be further revised, the study team will submit an amendment at DFCI and upon IRB approval, external sites will submit through local IRBs. Once the survey has been finalized, it will be disseminated to participants by the DFCI study team.

**Methods and Frequency of follow-up:** In order to reach a broad sample of patients who may be eligible for this study, the local study team will mail an initial letter (Appendix A) to a prospective patient. Because people are busy and may respond to different forms of communication (i.e. calls, brief insert notes, letters, etc.), the local study team will follow up with 3 additional contacts over an 8-week period to allow for sufficient time to respond. The DFCI study team will pilot two patient outreach materials from Patient Advocates—two brief notes—added to the invitation letter and survey to one hundred patients to test improved response and participation outcome. One or both of these outreach material, if proven effective, may be continued past the pilot one hundred patients. The DFCI study team has found this to be acceptable and desired in past survey research they have conducted. Participants who do not respond to Appendix A- Invitation letter and response form will be contacted at: 2 weeks (recontact), 4 weeks (call/resend) and 8 weeks (call/resend). If a participant returns Appendix A, her contact information and select case report form (CRF) information will be sent to the DFCI study team. Please see section 4.0 for the patient contact procedure after the study has closed to respond to patients who indicate interest to complete a new survey.

As outlined above, depending on modality of survey completion, the DFCI study team will collect the information as she is eligible, including: the screener, consent information and survey via her preferred method. There will be 3 potential recontact timepoints by the DFCI study staff to obtain consent/screener/survey from potential participants who do not complete the survey: 2 weeks (recontact), 4 weeks (call/resend) and 6 weeks (resend) from the initial contact. Participants who prefer to complete the survey via telephone will be mailed a copy of the paper survey and contacted up to 3 times to schedule the call to complete the survey.

**Translation of surveys.** The surveys will be offered in English, although a Spanish translation of Survey B.1 and B.2 will be available in paper format for mailing to patients. Translated documents will be submitted for IRB review prior to implementation. We will follow a method that ensures comparable levels of validity, reliability and cultural meaning. First, the English version will be translated into Spanish. Bilingual staff will then review the translation. We have expertise on the study team to lead this task. Certificates of translation will be obtained and submitted to the IRB with the translated material. Native speakers of other languages will be able to participate through a medical interpreter. All patients for whom English is not their primary language who have questions about the survey or study will also be able to utilize our institutional interpreter services.

### 5.5.2 Special Concerns

**Data Security.** The web-based survey has been developed in Research Electronic Data Capture (REDCap), a secure web-based software system that is compliant with HIPAA standards. Available to Duke, DFCI, MDACC, MGH, NWH, and DFCI @ SSH faculty, REDCap is commonly used for building and managing online databases and surveys. REDCap provides researchers with features that

facilitate both analytic and administrative competencies. These includes automated data download to Excel and common statistical packages (SPSS, SAS, Stata, R), a built-in project calendar, a scheduling module, and branching logic and range checks to reduce the potential of errors. Ad hoc reporting tools are available including frequencies and reports that can be generated at any time. The REDCap data centers are monitored 24/7 by an experienced team of engineers. They offer data redundancy through replicated databases and offer daily secure offsite backups.

**Data Privacy.** Only administrators, designated study staff, and customer/technical support managers will have access to survey data which will be stored in a password protected account. A written request from the patient to permanently remove all response data from the account will be answered in no more than two business days. If requested, all files, database records, and backups of this data will be destroyed. Data cannot be recovered after this is performed.

Participant data that is collected and stored in REDCap can be archived, which takes it offline and removes it from the DFCI study staff's list of projects. Once archived, it can only be accessed again by clicking the Show Archived Projects link at the bottom of the My Projects page.

### **5.5.3 Compensation**

As part of the informed consent process, participants will be notified that they will be offered a gift card worth \$20 as a token of appreciation for completion of the survey. This gift card will be mailed to them by Dana-Farber Cancer Institute study staff after survey completion.

## **5.6 Adverse Reactions and Their Management**

### **5.6.1 Reporting Adverse or Unanticipated Events**

Should there be a loss of confidentiality, reporting to the IRB will be performed in accordance with required policies.

### **5.6.2 Anticipated Reactions**

The survey being administered entails minimal physical and psychological risk on the part of the participants; however, it is also possible that answering certain questions might cause some distress. The CES-D will be scored within a week of receipt. Patients scoring  $\geq 16$  will be mailed a letter developed by Patient Advocates, Study PIs, and the CRC Staff within one calendar month providing support resources.

There is the potential loss of confidentiality, which will be managed by adherence to HIPAA regulations at all study sites.

### **5.6.3 Reaction Management**

It is possible that answering questions related to breast conditions may cause anxiety. In the letter of introduction, women are notified that they are free to skip any questions they do not want to answer.

Additionally, women are advised to contact their physicians or a study representative with any questions or concerns. If necessary, study staff will provide information on counseling services to patients that request assistance.

All members of the study team will be required to complete Human Subjects Protection Training. This requirement may be met by completing the NIH course, the CITI (Collaborative Institutional Training Initiative) program or another course as required by the member institution.

## **6.0 STATISTICAL ANALYSIS**

### **6.1 Primary and secondary endpoints**

Endpoints were selected with the input of patient stakeholders in the general categories of: 1) breast cancer and health-related clinical outcomes including pulmonary, cardiovascular, other cancer, and hematologic disease), and 2) Patient Reported Outcomes (PRO) which will include comprehensive domains of QOL and psychosocial outcomes, with a primary focus on pain and physical symptoms.

### **6.2 Sample size and statistical power**

Importantly, published data indicate that patients undergoing lumpectomy with radiation report comparable levels of pain and sensory disturbances as those undergoing mastectomy. Thus, these treatment groups will be grouped together in the initial analysis, then a stratified analysis will be performed. Preliminary data among 582 women undergoing either lumpectomy or mastectomy indicate that the mean persistent pain intensity after breast surgery is 2.61 (DS 4.24). Given a sample size of 900 patients in the GCC group and 300 in the AS group, we will be able to detect with 90% power at a level of 0.05 (2-sided) a difference in pain intensity score of 2 (from 2.61 to 0.61), which has been deemed to be a clinically meaningful difference.

Based upon the number of unique cases diagnosed with DCIS at each site between 2010 and 2013, we estimate that at all 6 study sites combined, approximately 1500 women will have been diagnosed with DCIS between January 1, 2012 and June 30, 2017 and will be eligible to participate. Our response rate in prior survey studies has been approximately 60% using the approach we will adapt to the current study; thus, we anticipate that about 900 women with DCIS will be accrued and will complete the survey across all study sites. These patients will be matched 3:1 to participants diagnosed with ADH or LCIS/ALH undergoing active surveillance. DCIS participants will be matched 3:1 to ADH/LCIS/ALH participants, based on matching criteria of age within 5 years, year of diagnosis, and study site. Additional matching criteria such as race, income, highest education level attained, and family history of breast cancer will be considered based upon stakeholder input during the protocol preparation process.

### **6.3 Analysis Plan: General Approach.**

We will conduct descriptive analyses to profile the samples, including examination of proportions, means, and medians, as well as estimates of variability such as standard errors, ranges, and confidence intervals. We will identify outlying observations. Continuous data distributions will be evaluated for appropriateness of scale, and normal score transformations will be used where appropriate. Appropriate summary statistics, histograms, scatter plots, or one- or two-way contingency tables for women of each

ethnic group will be computed. These analyses will be followed by bivariate analyses to examine the pairwise relationships among variables under examination. Demographic data will be compared for the respondents and non-respondents using chi-square or t-tests to assess selection bias. In addition to baseline disease and socio-demographic data, information relating to other treatment (e.g., endocrine treatment, radiation) as well as co-morbidities will be collected, allowing us to control for potential confounding by these factors. We will also analyze the decision-making, DCIS knowledge, and risk perception data at baseline and compare these domains between the GCC and ADH/LCIS/ALH/AS groups. We will also systematically collect and evaluate and report on the upstaging rates and associated details from initial diagnosis of DCIS.

**6.4 Management of missing data:** As with all studies there is a risk of biased statistical inference with missing data and we will adhere closely to standards put forth by the National Research Council. We will include details about missing patient data in all tables in subsequent analyses, and include a comparison of baseline characteristics of patients with and without missing data. We will carefully consider whether data missingness is random or whether missingness may be attributable to a certain factor and therefore not random (e.g., older women may be less likely to answer questions). We will assess non-response bias by comparing available characteristics in both patients and providers (e.g., practice type) among responders and non-responders.

6.0 STATISTICAL ANALYSIS

6.1 Primary and secondary endpoints

Endpoints were selected with the input of patient stakeholders in the general categories of: 1) breast cancer and health-related clinical outcomes including pulmonary, cardiovascular, other cancer, and hematologic disease), and 2) Patient Reported Outcomes (PRO) which will include comprehensive domains of QOL and psychosocial outcomes, with a primary focus on pain and physical symptoms.

6.2 Sample size and statistical power

Importantly, published data indicate that patients undergoing lumpectomy with radiation report comparable levels of pain and sensory disturbances as those undergoing mastectomy.⁵⁶ Thus, these treatment groups will be grouped together in the initial analysis, then a stratified analysis will be performed. Preliminary data among 582 women undergoing either lumpectomy or mastectomy indicate that the mean persistent pain intensity after breast surgery is 2.61 (DS 4.24).⁵⁵ Given a sample size of 900 patients in the GCC group and 300 in the AS group, we will be able to detect with 90% power at a level of 0.05 (2-sided) a difference in pain intensity score of 2 (from 2.61 to 0.61), which has been deemed to be a clinically meaningful difference.

Based upon the number of unique cases diagnosed with DCIS at each site between 2010 and 2013, we estimate that at all 6 study sites combined, approximately 1500 women will have been diagnosed with DCIS between January 1, 2012 and June 30, 2017 and will be eligible to participate. Our response rate in prior survey studies has been approximately 60% using the approach we will adapt to the current study; thus, we anticipate that about 900 women with DCIS will be accrued and will complete the survey across all study sites. These patients will be matched 3:1 to participants diagnosed with ADH or LCIS/ALH undergoing active surveillance. DCIS participants will be matched 3:1 to ADH/LCIS/ALH participants, based on matching criteria of age within 5 years, year of diagnosis, and study site. Additional matching criteria such as race, income, highest education level attained, and family history of breast cancer will be considered based upon stakeholder input during the protocol preparation process.

6.3 Analysis Plan: General Approach.

We will conduct descriptive analyses to profile the samples, including examination of proportions, means, and medians, as well as estimates of variability such as standard errors, ranges, and confidence intervals. We will identify outlying observations. Continuous data distributions will be evaluated for appropriateness of scale, and normal score transformations will be used where

appropriate. Appropriate summary statistics, histograms, scatter plots, or one- or two-way contingency tables for women of each ethnic group will be computed. These analyses will be followed by bivariate analyses to examine the pairwise relationships among variables under examination. Demographic data will be compared for the respondents and non-respondents using chi-square or t-tests to assess selection bias. In addition to baseline disease and socio-demographic data, information relating to other treatment (e.g., endocrine treatment, radiation) as well as comorbidities will be collected, allowing us to control for potential confounding by these factors. We will also analyze the decision-making, DCIS knowledge, and risk perception data at baseline and compare these domains between the GCC and ADH/LCIS/ALH/AS groups. We will also systematically collect and evaluate and report on the upstaging rates and associated details from initial diagnosis of DCIS.

6.4 Management of missing data: As with all studies there is a risk of biased statistical inference with missing data and we will adhere closely to standards put forth by the National Research Council.⁷⁷ We will include details about missing patient data in all tables in subsequent analyses, and include a comparison of baseline characteristics of patients with and without missing data. We will carefully consider whether data missingness is random or whether missingness may be attributable to a certain factor and therefore not random (e.g., older women may be less likely to answer questions). We will assess non-response bias by comparing available characteristics in both patients and providers (e.g., practice type) among responders and non-responders.

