## **2.2 Hypothesis and Specific Aims:**

We hypothesize that there are differences in patient-centered clinical outcomes and Patient Reported Outcomes (PROs) between women who choose GCC versus AS, and that these differences can be compared using advanced analytic methods to allow for the expected treatment selection biases between groups.

The specific aims of this study are the following:

**Aim 1. Compare patient-reported outcomes (PROs) between patients diagnosed with ductal carcinoma in situ (DCIS) who received GCC to patients diagnosed with DCIS who underwent AS as well as those diagnosed with atypical ductal hyperplasia (ADH), and lobular carcinoma in situ LCIS/atypical lobular hyperplasia (ALH) (as proxies for DCIS active surveillance (AS) group) in a cross-sectional patient cohort at 6 selected study sites.**

PROs will be collected from surveys administered to patients diagnosed for either DCIS, ADH, LCIS, or ALH between January 1, 2012 and June 30, 2017 at each of six study sites: Duke University Medical Center (DUMC), Dana-Farber Cancer Institute (DFCI), MD Anderson Cancer Center (MDACC), Massachusetts General Hospital (MGH), Newton Wellesley Hospital (NWH), and Dana-Farber/Brigham and Women's Cancer Center (DF/BWCC) in clinical affiliation with South Shore Hospital (DFCI @ SSH). We are planning for survey data collection to begin in September 2017, but will officially commence upon IRB approval at each recruiting site. MDACC received their site's IRB approval on December 6, 2017 and has now been added to the DFCI IRB as a site. MDACC will now complete applicable study procedures as outlined in this protocol. DUMC received their site's IRB approval on February 27, 2018 and has now been added to the DFCI IRB as a site. Duke will now complete study procedures as outlined in this protocol. MGH has been added to the DFCI IRB as a site. MGH will now complete study procedures as outlined in this protocol. DFCI @ SSH has been added to the DFCI IRB as a site. DFCI @ SSH will now complete study procedures as outlined in this protocol. The DFCI study team will complete all patient recruitment steps for DFCI @ SSH. NWH has been added to the DFCI IRB as a site. NWH will now complete study procedures as outlined in this protocol.

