#### ***Survey instrument/predictors:***

**Screening questions:** We will ask participants for their first date of DCIS/ADH/LCIS/ALH diagnosis; if they have had additional breast lesions since that initial breast lesion diagnosis; and if she has had any malignancy, other than non-melanoma skin cancer. Please see Appendix E (Screening questions) for reference.

**Socio-demographics:** Women will be asked about their race, education, employment and financial status using items selected from the **Alliance Patient Questionnaire** that is currently being piloted (Alliance A191401), adapted to include an item on employment status that has been tested previously in a breast cancer population and is going to be added to the next version of the Alliance Patient Questionnaire.

**Financial burden:** We will adapt items from the National Health Interview Survey and the Cancer Care Outcomes Research and Surveillance (CanCORS) Study to assess financial burden and impact on

employment-related metrics (e.g., sick leave, unpaid time off work).

**Medical, treatment, and family history:** We will survey women regarding their treatment history, including surgery type, radiation, and hormonal therapy use and adherence, as well as family history of breast/ovarian history. Specifically, we will adapt Part 1 of the Voils two-part measure of medication adherence, which includes 3 items that evaluates the extent of non-adherence over the past week.

We will assess co-morbidities using the Self-Administered Co-morbidity Questionnaire (based on Charlson Co-morbidity Index and other comorbidity indices).

**Pain:** the presence, severity, and functional impact of pain will be recorded as the primary QOL endpoint. The primary endpoint will be highest pain severity measured on a 10-point Likert scale and Pain Burden Index as measured by the Breast Cancer Pain Questionnaire (BCPQ). The BCPQ includes assessment of pain severity, pain frequency (how many days/week), and pain location (breast, arm, side, axilla), from which a Pain Burden Index (PBI) can be calculated. The BCPQ also includes questions about other body pain, seeking medical help for pain, and painkiller use. We will also use the Brief Pain Inventory, a well-validated general measure of pain and disability, worst pain, least pain, and interference with activities.

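### Section 6.2 states 90% power for a 2-point pain difference, but its own inputs give over 99.99% for an unadjusted comparison

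*SAP*

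**What the plan says.** Section 6.2 has the same text in the Protocol and the SAP, and it holds the only power statement in either document. From preliminary data on 582 women it reports that "the mean persistent pain intensity after breast surgery is 2.61 (DS 4.24" (DS is presumably SD). It then gives the group sizes, "Given a sample size of 900 patients in the GCC group and 300 in the AS group", and concludes that "we will be able to detect with 90% power at a level of 0.05 (2-sided) a difference in pain intensity score of 2". The 2 points are the gap between a GCC mean of 2.61 and an AS mean of 0.61, and the section calls this clinically meaningful.

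The 900 is a feasibility figure: about 1,500 eligible women at 60% response, so that "we anticipate that about 900 women with DCIS will be accrued and will complete the survey across all study sites". The comparison group follows from the ratio: "These patients will be matched 3:1 to participants diagnosed with ADH or LCIS/ALH undergoing active surveillance".

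Two other places bear on the calculation. Protocol section 5.2 (Pain) says: "The primary endpoint will be highest pain severity measured on a 10-point Likert scale and Pain Burden Index". Protocol section 2.2 expects that "these differences can be compared using advanced analytic methods to allow for the expected treatment selection biases between groups".

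Section 6.2 names no test and gives no separate SD for the AS group. It also gives no design effect for matching and no variance inflation for adjustment.

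**The concern.** The sentence presents sample size, significance level, difference and power as one calculation, and they do not fit together. With 1,200 women and an SD of 4.24, a 2-point difference is about seven standard errors, far more than 90% power requires.

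What is at stake is how the pain result will be read. A reader of section 6.2 would think the study is sized to find differences of about 2 points. On the stated inputs, an unadjusted comparison has 90% power for less than half of that. An observed difference of about 0.55 points, roughly a quarter of the difference the plan calls clinically meaningful, would reach p < 0.05. The text should make clear that statistical significance can occur well below the clinical threshold.

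The mismatch also raises the question whether the SD of 4.24 belongs to the pain score at all.

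**Working it through.** **Inputs, all from section 6.2:** n = 900 (GCC) and 300 (AS); two-sided alpha 0.05; difference 2 points (2.61 against 0.61); SD 4.24. The SD is assumed common to both groups because only one is given. The 900 are already expected completers (1,500 × 0.60 = 900), so no further loss is taken off.

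**Attempt to reproduce the 90%**

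- SE = 4.24 × √(1/900 + 1/300) = 4.24 × 0.06667 = 0.2827.
- 2 / SE = 7.075.
- Power = Φ(7.075 − 1.960) = Φ(5.115) = 0.9999998. The noncentral t with 1,198 df gives the same value.

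The stated figure is not reproduced. Other readings do not reach it either:

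| Variant | Power for 2 points |
|---|---|
| One-sided test | 0.99999997 |
| Rank test, worst-case efficiency 0.864 | 0.999998 |
| Alpha 0.025 (e.g. two primary measures) | 0.9999993 |
| Alpha 0.001 | 0.99992 |
| 900 in total, split 675/225 | 0.99998 |
| 60% response applied a second time, 540/180 | 0.9998 |

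**What would give 90%** (multiplier 1.960 + 1.2816 = 3.2415)

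- Difference: 3.2415 × 0.2827 = 0.916 points.
- SD: (2 / 3.2415) / 0.06667 = 9.25.
- Variance inflation: (9.25 / 4.24)² = 4.76.
- Sample size at 3:1: 63 AS and 189 GCC women.

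The smallest observed difference that reaches p < 0.05 is 1.960 × 0.2827 = 0.554 points.

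**Does the SD matter?** Assume the 10-point scale runs 0–10. The documents do not say so, but an AS mean of 0.61 is impossible on 1–10. The largest SD at mean m is √(m(10 − m)).

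- Overall maximum, 5 in both groups: SE = 5 × 0.06667 = 0.3333; power = Φ(6 − 1.960) = 0.99997; 90%-power difference = 3.2415 × 0.3333 = 1.08.
- At mean 2.61: √(2.61 × 7.39) = 4.39, so 4.24 is possible but close to the limit.
- At mean 0.61: √(0.61 × 9.39) = 2.39, so 4.24 is not possible in the AS group.

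To respect that limit, keep 4.24 in GCC and let the AS SD sit at its ceiling for the AS mean 2.61 − d. Then solve d = k × √(4.24²/900 + (2.61 − d)(7.39 + d)/300):

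- k = 3.2415 gives d = 0.85 (AS mean 1.76, ceiling 3.81).
- k = 1.960 gives d = 0.54 (AS mean 2.07, ceiling 4.05).

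**Allowing for matching, weighting or adjustment.** The inflation factors v are assumptions; SE = 0.2827 × √v.

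| v | Power for 2 points | 90%-power difference |
|---|---|---|
| 1.5 | 0.9999 | 1.12 |
| 2 | 0.9988 | 1.30 |
| 3 | 0.983 | 1.59 |
| 4 | 0.943 | 1.83 |
| 4.76 | 0.90 | 2.00 |

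**The case against.** There are four fair points on the other side.

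- **90% could mean at least 90%.** Read that way, the sentence is true on its inputs. But it does not say at least, and on that reading the section still does not tell the reader what difference the study can detect with 90% power.
- **The unadjusted comparison may not be the main analysis.** The plan intends matching, control for confounders and methods for selection bias, and the precision after these steps is unknown. This stands, so the recomputed figures apply only to an unadjusted pooled comparison. It does not rescue the 90%: section 6.2 mentions no inflation, and about 4.8-fold would be needed.
- **The 0.92 rests on an SD that a 0–10 score cannot have in the AS group.** This also stands. A difference of 0.92 puts the AS mean at 2.61 − 0.92 = 1.69, where the ceiling is √(1.69 × 8.31) = 3.75. The 0.85 is a bound too, since it has every AS woman scoring 0 or 10. Both figures are conditional, and neither is final until the SD is confirmed.
- **Nothing depends on the error.** The 900 comes from eligibility and response, and the 2-point target is not underpowered. This is why the point is minor.

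**Conclusion.** The concern holds, as a minor and conservative error. On section 6.2's own inputs, unadjusted power for 2 points is over 99.99%, not 90%. The 90%-power difference is about 0.92 points with SD 4.24 in both groups, or about 0.85 if the AS SD is limited by a 0–10 scale.

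These figures assume two independent groups of 900 and 300 and no design effect. If the score runs 0–10, the direction does not depend on the printed SD: power is at least 99.997%, and the 90%-power difference at most 1.08 points.

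One reservation concerns the scale of the SD. The primary endpoint also includes the Pain Burden Index, whose range the documents do not give. If 4.24 belongs to that index, the 0–10 limits do not apply and the inputs mix two measures. The documents alone cannot settle this. The check covers the pooled pain comparison only, not the stratified analysis or the index itself.

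**What to change.** In section 6.2 of both documents:

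1. Check the SD of 4.24, and the scale it was measured on, against the cited source. State the SD assumed for each group.
2. Replace the 90% with the power for 2 points recomputed from the confirmed SDs, labelled as the unadjusted pooled GCC versus AS comparison. Give the 90%-power difference beside it. On the current inputs the power is over 99.9%, with the difference as given in the verdict for each SD assumption.
3. Add that matching, weighting or covariate adjustment may change this precision, with an illustration. For example, an assumed variance inflation of 2 would give 99.88% power and a 90%-power difference of about 1.30 points.

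This costs wording in one section of each document. Sample size, recruitment, data collection and analyses do not change.
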